### 3.6.5 Statistical Analysis

Details of all statistical analyses will be described in a statistical analysis plan. All data collected will be presented in data listings. Data from subjects excluded from an analysis population will be presented in the data listings but not included in the calculation of summary statistics.

Data from subjects who received placebo will be pooled across cohorts for all treatments.

For categorical variables, frequencies and percentages will be presented. Continuous variables will be summarized using descriptive statistics (number of subjects, mean, median, SD, minimum, and maximum).

#### 3.6.5.1 Immunogenicity Analyses

The following immunogenicity outcome measures (for serum neutralizing antibody titers) and their 95% CIs, where appropriate, will be summarized by treatment group and by visits after each vaccination:

- Geometric mean titer (GMT) of anti-Zika virus neutralizing antibodies (PRNT50 assay)
  - Part A: At Baseline (pre-vaccination at Visit 1) and on 28 days after both first and second vaccination (Visits 4 and 7, respectively)
  - Part B: At 168 ( $\pm 15$ ) days and 364 ( $+15$ ) days (Visits 12 and 19, respectively) will be evaluated if interim immunogenicity analyses warrants long term analyses of persistence.
- Geometric mean ratio (GMR)Post/Pre
  - Part A and Part B: The ratio of post-vaccination GMT to pre-vaccination (Visit 1) GMT of subjects who have a baseline sample (pre-vaccination at Visit 1) and post-vaccination sample at any post-dose time point (Visits 4, 7, 12, or 19; data from visits 12 and 19 will be included only if based on interim immunogenicity analyses results the evaluation of these later timepoints is warranted.)
- Seroconversion

- Part A: The proportion of subjects with Zika virus PRNT50 titer  $\geq 1:10$ ,  $\geq 1:20$ ,  $\geq 1:40$ ,  $\geq 1:80$ ,  $\geq 1:160$ , and  $\geq 1:320$  at Baseline, Visit 4, and Visit 7
- Part A: The proportion of subjects with baseline Zika virus PRNT50 titer  $< 1:10$  and post-vaccination Zika virus PRNT50 titer of  $\geq 1:20$ ; or with baseline Zika virus PRNT50 titer  $\geq 1:10$  and with post-vaccination 4-fold titer increase (Visits 4 or 7)
- Part B: The proportion of subjects who maintained seroconversion status at specific time points of 168 ( $\pm 15$ ) days and 364 ( $+15$ ) days (Visits 12 and 19, respectively). Data from visits 12 and 19 will be included only if based on interim immunogenicity analyses results the evaluation of these later timepoints is warranted.
- Cross-Stimulation with prior flavivirus vaccination (subset of flavivirus-seropositive subjects)
  - Part A:
    - Geometric mean titer (GMT) of anti-yellow fever neutralizing antibodies at Baseline, Visit 4, and Visit 7
    - Geometric mean ratio (Post/Pre) of anti-yellow fever neutralizing antibodies at Visit 4 and Visit 7
    - The proportion of subjects with anti-yellow fever antibody titer  $\geq 1:10$ ,  $\geq 1:20$ ,  $\geq 1:40$ ,  $\geq 1:80$ ,  $\geq 1:160$ , and  $\geq 1:320$  at Baseline, Visit 4, and Visit 7
    - Additional neutralization assays for other flavivirus may be performed in select subsets

### 3.6.5.2 Safety Analyses

Data from subjects who received placebo will be pooled across cohorts for all treatments. Reactogenicity will be summarized by treatment assignment (10-, 25-, or 100- $\mu\text{g}$  mRNA-1325 or placebo), vaccination (first or second), duration, and severity. Adverse events will be coded by preferred term and system organ class using MedDRA and summarized by part, treatment assignment, vaccination (first or second), and overall. Adverse events will also be summarized by severity and relationship to the study vaccine. Descriptive statistics will be presented and the difference in the proportion of subjects with AEs will be provided comparing each dose

level with placebo recipients across all groups. Individual subject listings will be provided for all AEs, AEs leading to study withdrawal, AESIs, medically attended AEs, and SAEs.

Safety data from clinical laboratory test results and vital sign measurements will be graded by severity scoring and analyzed by treatment group and vaccination (first or second). Absolute and change from baseline values will be provided according to the toxicity table, along with mean, median, and standard deviation. Results of serology, urine drug screen, and pregnancy tests will be listed for all subjects randomly assigned to receive study treatment.

Medical history data for all subjects randomly assigned to receive study treatment will be presented by subject in a listing.

Baseline demographic and background variables will be summarized by treatment group and cohort for all subjects. The number of subjects who enroll in the study and the number and percentage of subjects who complete the study will be presented. Frequency and percentage of subjects who withdraw or discontinue from the study, and the reason for withdrawal or discontinuation, will also be summarized.

Prior and concomitant medication will be listed (with start and stop dates) for each subject and summarized by common medical dictionary coding. Any vaccinations that occur during the trial conduct will also be captured and summarized.

### **3.6.6 Handling of Missing Data**

For GMT calculation, antibody values reported as below the lower limit of quantification (LLOQ) will be replaced by  $0.5 \times \text{LLOQ}$ . For fold-rise, values  $< \text{LLOQ}$  will be replaced by  $0.5 \times \text{LLOQ}$  for a numerator and by LLOQ for a denominator. If both the numerator and denominator are  $< \text{LLOQ}$ , then both will be converted in the same way. Values that are greater than the upper limit of quantification (ULOQ) will be converted to the ULOQ. Missing results will not be imputed.

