### **2.2 Secondary Objective**

The secondary objective of this study is to assess the immunogenicity of a range of doses of mRNA-1325 Zika vaccine and to select a dose for further development, based on changes from Baseline in the following tests:

- ZikaV-specific neutralizing antibody titers measured by a Plaque Reduction Neutralizing Titer EC50 (PRNT50);

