### **3.6.7 Interim Analyses**

Following completion of each cohort in Part A, the database will be locked for that cohort and safety and immune test results will be analyzed through 28 days following the second vaccination. As dose escalation occurs, cumulative analyses will be included for each subsequent data lock to allow for all prior dosing cohorts to be analyzed by cohort, treatment

assignment, and in aggregate for mRNA-1325 exposure. Immunogenicity and safety data, including mean group analyses of change from Baseline, where applicable, will be summarized for each dose cohort. These data are required to inform decisions on dose selection for this and other development programs using the same mRNA platform. Subject-level treatment assignment will not be released to the subjects or to those individuals involved in managing or assessing safety in Part B of the study until that portion of the study is completed.

Additional information can be found in the statistical analysis plan.

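### Does Section 3.6.6 leave it open which below-LLOQ substitution applies to the post/pre geometric mean ratio?

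*Protocol*

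**What the plan says.** Section 3.6.6 of the protocol has two sentences on values below the LLOQ. The first reads "For GMT calculation, antibody values reported as below the lower limit of quantification (LLOQ) will be replaced by" 0.5×LLOQ. The second concerns fold-rise: such values are replaced by 0.5×LLOQ "for a numerator and by LLOQ for a denominator". If both members of the pair are below the LLOQ, "then both will be converted in the same way". GMR is not mentioned, and no numeric LLOQ is given.

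Section 3.6.5.1 (and the synopsis) defines the Zika GMR as "The ratio of post-vaccination GMT to pre-vaccination (Visit 1) GMT of subjects who have a baseline sample" and a post-vaccination sample. The yellow fever measure appears further down the same list as "Geometric mean ratio (Post/Pre) of anti-yellow fever neutralizing antibodies at Visit 4 and Visit 7", without a definition of its own.

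Two other places give the measure its weight. The secondary objective (Section 2.2) is to assess immunogenicity and "to select a dose for further development, based on changes from Baseline in the following tests". Section 3.6.7 says that immunogenicity and safety data, "including mean group analyses of change from Baseline, where applicable, will be summarized for each dose cohort", and that these data inform dose selection. Section 3.6.5 leaves the details of all analyses to the SAP.

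**The concern.** In paired subjects, a ratio of GMTs equals the geometric mean of the individual post/pre ratios, provided the same substitution is used in both. So the GMR looks like a group-level fold-rise, and both rules in Section 3.6.6 could seem to cover it. They do not give the same number, because one puts 0.5×LLOQ in the denominator and the other puts the full LLOQ there.

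If an analyst applied the fold-rise rule, three things would follow:

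- The GMR would no longer equal the ratio of the reported GMTs.
- Contrasts between doses with different response rates would be compressed, and two close doses could change order.
- A group with no true change and titres near the LLOQ would score below 1.

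About two-thirds of each cohort is flavivirus naïve and likely to start below the LLOQ, so the affected share could be large. The plan uses change from Baseline to inform the choice of dose, so a descriptive measure that could move by up to 2-fold deserves a check.

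**Working it through.** **Inputs.** There are 24 subjects on mRNA-1325 per cohort (Section 3.1), of whom about two-thirds are flavivirus naïve (Section 3.4.1), so about 24 × 2/3 = 16. The substitution rules are those of Section 3.6.6, and the GMR definition is that of Section 3.6.5.1. The protocol states no figure to reproduce. The LLOQ is not stated; 1:10 is assumed in the titre examples, but the 2^p result does not depend on it.

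**Step 1: which rule the text selects.** The GMR is defined as one GMT divided by another. Calculating a GMT requires 0.5×LLOQ for values below the LLOQ. Both parts of the ratio are GMTs, so both take 0.5×LLOQ. The fold-rise sentence is not needed to compute the measure as defined.

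**Step 2: how far apart the rules are.** Write L for the LLOQ and compare each subject's post/pre ratio.

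| Pre | Post | GMT rule | Fold-rise rule |
|---|---|---|---|
| ≥L | ≥L | post/pre | post/pre |
| ≥L | <L | 0.5L/pre | 0.5L/pre |
| <L | <L | 1 | 1 |
| <L | ≥L | post/(0.5L) | post/L |

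Only the last row differs, by a factor of 2. Over a group,

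GMR(GMT rule) / GMR(fold-rise rule) = 2^p, with p the share of paired subjects in the last row.

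| p | 0 | 0.25 | 0.50 | 0.667 | 0.75 | 1 |
|---|---|---|---|---|---|---|
| 2^p | 1.00 | 1.19 | 1.41 | 1.59 | 1.68 | 2.00 |

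If all 16 naïve subjects of 24 move from below the LLOQ to at or above it and no one else does, p = 0.667 and the factor is 1.59. For scale, at p = 1 the shift is 1.0 log2. The 95% CI half-width at n = 16 is t(0.975, 15) × SD/√16 = 2.131 × SD/4, which is 0.53 to 1.07 log2 for an assumed SD of 1 to 2 log2. If the sentence on double negatives were read as applying the asymmetric substitution there too, the third row would be 0.5 under the fold-rise rule. The exponent would then be the share of all subjects with pre <L, and the ceiling would still be 2.

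**Step 3: contrasts between doses.** Under the fold-rise rule the ratio of the higher-responding dose's GMR to the other's is multiplied by 2^(−d), where d is the difference in p. This is 1.00 when response is equal, 2^(−0.2) = 0.87 at 20 points and 2^(−0.4) = 0.76 at 40 points.

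**Step 4: can the order reverse?** Take 16 subjects per dose, all baselines <LLOQ and L = 10. On dose X, 10/16 respond at 1:160; on dose Y, 13/16 respond at 1:80.

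- GMT rule: X has mean log2 = (10/16) × log2(160/5) = 0.625 × 5 = 3.125, so GMR 8.72. Y has (13/16) × log2(80/5) = 0.8125 × 4 = 3.25, so GMR 9.51.
- Fold-rise rule: X has 0.625 × log2(160/10) = 0.625 × 4 = 2.5, so 5.66. Y has 0.8125 × 3 = 2.4375, so 5.42.

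The order does reverse. The size of the gap shows how little that means. Under the GMT rule the SDs are 5 × √(0.625 × 0.375 × 16/15) = 2.5 and 4 × √(0.8125 × 0.1875 × 16/15) = 1.61. The SE of the difference is √((2.5² + 1.61²)/16) = 0.74, and the gap is 0.125/0.74 = 0.17 SE. Under the fold-rise rule the SDs are 2.0 and 1.21, the SE is 0.58, and the gap is 0.0625/0.58 = 0.11 SE. Neither ranking says anything about the doses.

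**Step 5: a group with no change.** With independent readings around a common mean and probability π of reading below the LLOQ, the last row has probability π(1 − π). The fold-rise GMR is then 2^(−π(1−π)): 0.84 at π = 0.5, 0.94 at 0.9, 0.99 at 0.99. The GMT rule gives 1.00 throughout. The effect exists only under the reading that the definition does not support, and it fades once nearly everyone is below the LLOQ.

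**Step 6: what else is touched.** GMTs and titre-threshold proportions do not use the fold-rise rule. Seroconversion from a baseline below 1:10 is judged on an absolute titre, and the 4-fold criterion applies only from 1:10 upward. If the LLOQ is 1:10 or lower, no substituted denominator enters it.

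**The case for a change.** The strongest case for a change starts from the fold-rise sentence. If the GMR takes the GMT rule and the LLOQ is 1:10 or lower, the LLOQ-denominator clause governs nothing listed in Section 3.6.5.1, which could suggest it was written with the GMR in mind. The yellow fever GMR has no definition of its own, and the change-from-Baseline summaries in Section 3.6.7 are undefined. The protocol did not leave the matter blank for the SAP; it fixed two rules, and an SAP using either could claim to follow it. The measure also counts in practice: Section 1.5 records that the Cohort 4 dose was changed after a look at Cohort 2 immunogenicity.

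What stands is that Section 3.6.6 does not mention the GMR, and that the wrong choice would be visible in the numbers.

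The rest is weaker. That the fold-rise clause has little to do depends on an LLOQ the protocol does not state, and a rule with little work is not evidence that it overrides a definition given elsewhere. The yellow fever GMR carries the same label, in the same list, as the Zika GMR defined above it, so reading it the same way is natural. Spelling out the Section 3.6.7 summaries is ordinary SAP work. Imposing 0.5×LLOQ on individual fold-rises as well would override an explicit, conservative convention and give up its lower-bound property in baseline-negative subjects.

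**Conclusion.** No change to the plan is needed. Followed as written, the protocol gives the Zika GMR as a ratio of two GMTs, each with 0.5×LLOQ for values below the LLOQ. That is the symmetric version and it agrees with the reported GMTs. The yellow fever GMR takes the same definition by its label and position. The gap is a missing cross-reference that a statistician programming the tables fills sensibly from Section 3.6.5.1.

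The 2^p factor, at most 2-fold and about 1.59 if 16 of 24 active subjects move from below to at or above the LLOQ, measures what would happen if the definition were set aside. It is not an error in the planned analysis. Even then it would affect a descriptive summary reported beside GMTs and threshold proportions that do not move. No formal test or numeric dose-selection rule uses the GMR, and the rank reversal needs doses that the data could not separate anyway.

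The 2^p result holds for any LLOQ if a pair with both values below it scores 1. The titre examples and the statement on seroconversion assume an LLOQ of 1:10 (or lower, for seroconversion). The interval widths assume a log2 SD of 1 to 2. The SAP was not available for this check and may already make the link explicit.

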### **3.6.7 Interim Analyses**

Following completion of each cohort in Part A, the database will be locked for that cohort and safety and immune test results will be analyzed through 28 days following the second vaccination. As dose escalation occurs, cumulative analyses will be included for each subsequent data lock to allow for all prior dosing cohorts to be analyzed by cohort, treatment

assignment, and in aggregate for mRNA-1325 exposure. Immunogenicity and safety data, including mean group analyses of change from Baseline, where applicable, will be summarized for each dose cohort. These data are required to inform decisions on dose selection for this and other development programs using the same mRNA platform. Subject-level treatment assignment will not be released to the subjects or to those individuals involved in managing or assessing safety in Part B of the study until that portion of the study is completed.

Additional information can be found in the statistical analysis plan.

### **3.7 Data Quality Assurance**

All aspects of the study will be monitored for compliance with applicable government regulations with respect to current ICH harmonised tripartite guideline E6(R1): Good Clinical Practice and current standard operating procedures. The eCRFs will be utilized and accessed through iMedidata® via the internet. This electronic data capture system is validated and compliant with US Title 21 of CFR Part 11. Each person involved with the study will have an individual identification code and password that allow for record traceability. There may be an internal quality review audit of the data and additional reviews by the clinical monitor.

Due to safety review requirements, no more than 3 business days should transpire between subject data availability (visits, laboratory test results, etc) and data entry. As a quality measure, timeliness of data entry and data query resolution will be reported to the IST. Other issues of data quality that may hinder safety review or pose a concern with patient safety will also be reported to the IST with appropriate awareness to the SMC if needed.

## **4 Investigator Obligations**

The following administrative items are meant to guide the investigator in the conduct of the study and may be subject to change based on industry and government standard operating procedures, working practice documents, or guidelines. Changes will be reported to the IRB but will not result in protocol amendments.

### **4.1 Confidentiality**

All laboratory specimens, evaluation forms, reports, and other records will be identified in a manner designed to maintain subject confidentiality. All records will be kept in a secure storage area with limited access. Clinical information will not be released without the written permission of the subject, except as necessary for monitoring and auditing by the Sponsor, its designee, relevant regulatory authority, or the IRB.

The investigator and all employees and coworkers involved with this study may not disclose or use for any purpose other than performance of the study, any data, record, or other unpublished, confidential information disclosed to those individuals for the purpose of the study. Prior written agreement from the Sponsor or its designee must be obtained for the disclosure of any said confidential information to other parties.

### **4.2 Institutional Review**

Federal regulations and the ICH E6(R1) guidelines require that approval be obtained from an IRB before participation of human subjects in research studies. Before study onset, the protocol, informed consent, advertisements to be used for the recruitment of study subjects, and any other written information regarding this study to be provided to the subject must be approved by the IRB. Documentation of all IRB approvals and of the IRB compliance with the ICH E6(R1) guidelines will be maintained by the site and will be available for review by the Sponsor or its designee.

All IRB approvals should be signed by the IRB chairman or designee and must identify the IRB name and address, the clinical protocol by title or protocol number or both and the date approval or a favorable opinion was granted.

### **4.3 Subject Consent**

Written informed consent in compliance with US Title 21 CFR Part 50 shall be obtained from each subject before he or she enters the study or before any unusual or non-routine procedure that involves risk to the subject are performed. If any institution-specific modifications to study-related procedures are proposed or made by the site, the consent should be reviewed by the Sponsor or its designee or both before IRB submission. Once reviewed, the investigator will submit the ICF to the IRB for review and approval before the start of the study. If the ICF is revised during the course of the study, all active participating subjects must sign the revised form.

Before recruitment and enrollment, each prospective subject will be given a full explanation of the study and be allowed to read the approved ICF. Once the investigator is assured that the subject understands the implications of participating in the study, the subject will be asked to give his or her consent to participate in the study by signing the ICF. A separate counseling and consent for HIV testing will occur.

The ICF will also explain that excess serum from immunogenicity testing may be used for future research which may be performed at the discretion of the Sponsor to better characterize the immune response to the ZikaV protein (inclusive of further T- and B-cell responses, additional assay development, and the immune response across flaviviruses).

The investigator or designee will provide a copy of the ICF to the subject. The original form shall be maintained in the subject's medical records at the site.

### **4.4 Study Reporting Requirements**

By participating in this study the investigator agrees to submit reports of SAEs and AESIs according to the time line and method outlined in this protocol. In addition, the investigator agrees to submit annual reports to his or her IRB as appropriate.

### **4.5 Financial Disclosure and Obligations**

The investigator is required to provide financial disclosure information to allow the Sponsor to submit the complete and accurate certification or disclosure statements required under 21 CFR 54. In addition, the investigator must provide to the Sponsor a commitment to promptly update this information if any relevant changes occur during the course of the investigation and for 1 year following the completion of the study.

Neither the Sponsor, PPD, nor the study site is financially responsible for further testing or treatment of any medical condition that may be detected during the screening process. In addition, in the absence of specific arrangements, neither the Sponsor, PPD, nor the study site is financially responsible for further treatment of the disease under study.

#### **4.6 Investigator Documentation**

Prior to beginning the study, the investigator will be asked to comply with ICH E6(R1) 8.2 and Title 21 of the CFR by providing the following essential documents, including but not limited to:

- IRB approval,
- An original investigator-signed investigator agreement page of the protocol,
- Form FDA 1572, fully executed, and all updates on a new fully executed Form FDA 1572,
- Curriculum vitae for the principal investigator and each subinvestigator listed on Form FDA 1572. Current licensure must be noted on the curriculum vitae. The curriculum vitae will be signed and dated by the principal investigators and subinvestigators at study start-up, indicating that they are accurate and current,
- Financial disclosure information to allow the Sponsor to submit complete and accurate certification or disclosure statements required under 21 CFR 54. In addition, the investigators must provide to the Sponsor a commitment to promptly update this information if any relevant changes occur during the course of the investigation and for 1 year after the completion of the study,
- An IRB-approved ICF, samples of site advertisements for recruitment for this study, and any other written information about this study that is to be provided to the subject, and
- Laboratory certifications and reference ranges for any local laboratories used by the site, in accordance with 42 CFR 493.

